9.2.2. Sample Size Re-estimation

At interim analyses 2, 3 and 4 (see Section 9.5) the sample size may be re-estimated based on emerging data. This will be based on the change from baseline in the continuous Mayo score. The sample size may need to be re-estimated if higher variability or differing placebo means are observed compared to those the study has been designed on. Therefore, any significant deviation from the assumptions used to power the study may result in changes to the study population including the number of participants to be randomized.

As part of this re-estimation if the distribution of the advanced therapy experience status (naïve or experienced) is unbalanced across the treatment groups then the recruitment strategy may be altered to establish a balance. A maximum of 320 participants could be randomized into the study following this sample size re-estimation.

9.3. Populations for Analyses

For purposes of analysis, the following populations are defined:

Population	Description
Enrolled	All participants who sign the ICF and were screened for eligibility.
Randomized	All participants who were randomly assigned to treatment in the study.
Safety	All randomized participants who receive at least 1 dose of study treatment.
PK	All participants in the Safety population who had at least 1 non-missing PK assessment (non-quantifiable values will be considered as non-missing values).
Intent to Treat Exposed (ITTE)	The ITTE population is defined as all participants who were randomised to treatment, who received at least one dose of study medication and who have at least one valid post dose assessment.

Population	Description
Per Protocol (PP)	
The PP Population is defined as all participants who are included in the ITTE population and are not major protocol violators with regards to inclusion/exclusion criteria, investigational product compliance and concomitant medication instructions, as defined in the RAP.
 
Participants to be excluded from the PP population will be identified prior to randomisation being unblinded or any data evaluation being performed.

9.4. Statistical Analyses

The Induction Phase and Extended Treatment Phase will be reported separately, where the primary and secondary analyses are based on the Weeks 0-10 of the Induction Phase.

9.4.1. Efficacy Analyses

Endpoint	Statistical Analysis Methods
Primary (efficacy)	
 Bayesian dose-response analyses will be conducted for change from baseline in the Complete 4-domain Mayo score at Week 10. The data will be initially analysed using an Emax model of the form: $Y = E0 + Emax * (Di)^\gamma / \{ ED50^\gamma + (Di)^\gamma \}$; where E0 is the minimum dose effect, Emax is the maximum achievable effect above placebo, ED50 is the dose at half Emax, Di are doses =0, 45, 150, 300, 450mg and γ is the slope parameter (shape of the potential sigmoid dose-response curve). Y is a measure of change from baseline in Mayo continuous score. Initially, normal vague priors will be used for E0, γ and Emax: Normal(0, sd=100). A functional uniform prior will be used for ED50 and h (Bornkamp, 2014), where the prior density for the functional uniform prior is based on all the parameters in the model. The parameterisation of the priors used in the analysis will be reported in the clinical study report. The primary dose-response model is the 4-parameter Emax model. Additional models will also be investigated: 3-parameter Emax model, power model, linear, quadratic, log-transformed dose. Each of the models will be fitted to the data and their fit compared using the Deviance Information Criterion (DIC). The model with the lowest DIC will be the primary model for inference if it shows a DIC difference from the 4-parameter Emax of at least 5. A four parameter Emax dose-response model, once fitted, will be used to estimate the minimally effective dose and 95% credible interval of each dose level relative to placebo.

Endpoint	Statistical Analysis Methods
	
 • If the four parameter Emax model is not applicable then additional models will be investigated: three parameter Emax model, power model, linear, quadratic, log-transformed dose. Each of the models will be fitted to the data and their fit compared using the Deviance Information Criterion (DIC), where the model with the lowest DIC will be the primary model for inference. • Prior medication will be included as a stratification factor: advanced therapy naïve, experienced a single class of advanced therapy, or experienced multiple classes of advanced therapies. • Further details of the Emax model will be defined in the RAP. • The primary analysis will use the ITTE analysis population. • The primary estimand will use a treatment policy strategy for intercurrent events, with the exception of discontinuations due to COVID-19 pandemic which will use a hypothetical strategy. • Under the hypothetical strategy, data set to missing would be assumed to be missing at random (MAR).
Secondary	
 • Analyses of the secondary endpoints will be conducted using similar methodology as for the primary endpoint (with an appropriate link-function for binary endpoints). • The decision criteria at the interim analyses 3 and following completion of the primary analysis will primarily be based on the proportion of participants who achieve endoscopic healing. These are based on predictive probabilities based on the data available. Details are outlined in Section 9.5, and in the interim analysis charter and RAP.
Exploratory	
 • Will be described in the RAP.

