9. STATISTICAL CONSIDERATIONS

9.1. Statistical Hypotheses

The first primary objective of this study is to assess the safety and tolerability of GSK2831781 in participants with moderate to severe UC. No formal hypotheses will be tested for this objective.

The second primary objective of this study is to evaluate the dose-response relationship in the change from baseline in the Complete 4-domain Mayo score, following 10 weeks of treatment with GSK2831781 or placebo. The dose response relationship will be characterised using the posterior probabilities of the parameters of an Emax model and by estimating the response at each dose level, using Bayesian methodologies, this will be the primary efficacy analysis. The primary efficacy analysis will therefore not use frequentist hypothesis testing, a characteristic of a well fitted model will be that the half width of the 95% credible interval for the change from baseline in Complete 4-domain Mayo response at ED90 is ≤ 1 . The dose-response relationship will also be assessed for selected categorical secondary endpoints (Endoscopic Improvement, Clinical Response and Clinical Remission).

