9.2. Sample Size Determination

9.2.1. Sample Size Assumptions

Approximately 242 participants will be randomly assigned to study intervention under the assumption that a proportion will not be able to provide a Week 10 Complete 4-domain Mayo score assessment under the additional (hypothetical) estimand. If the attrition rate is higher than planned for (e.g., 15% or more) then additional participants, up to a maximum of 320, may be recruited.

Primary Analysis: Dose-response change from baseline in Mayo score

[figure not shown]
At Week 10 the expected distribution of the change from baseline in the continuous Mayo score in the placebo group is a mean of -1 and a standard deviation of 1.5 (based on tofacitinib Phase II data [[Sandborn](#), 2012]). Based on these assumptions the proposed sample size of 68 participants on the GSK2831781 450mg dose level, 42 participants on each of the GSK2831781 lower dose levels, and 48 participants on placebo are sufficient to characterise the dose-response curve. This is based on 5000 simulated trials where the following Emax model was fitted to simulated data:

$$Y = E0 + Emax * (Di)^\gamma / \{ED50^\gamma + (Di)^\gamma\}$$

Where E0 is the minimum dose effect, Emax is the maximum achievable effect above placebo, ED50 is the dose at half Emax, Di are doses = 0, 45, 150, 300, 450 and γ is the slope parameter (shape of the potential dose response curve). Y is the change from baseline in the continuous Mayo score. E0 is the assumed effect with Dose=0 (placebo) which is -1, the Emax is taken as -3, γ is assumed to be 1 and ED50 is assumed to be 100.

For the E0 and Emax parameters a normal prior with mean 0 and standard deviation of 100 was used. For ED50 a beta(0.5, 5.2) was used scaled between 0 and 675 (1.5*top dose, as suggested by [Bornkamp](#), 2014 as an approximation to the functional uniform prior). For the standard deviation a gamma (shape=2, rate=0.1) was used ([Chung](#), 2013).

[Figure 4](#) below illustrates a sample of fitted model curves. In these simulations the half width of the 95% credible interval for the Complete Mayo response at ED90 is ≤ 1 97% of the time:

Figure 4 Dose-response precision based on outlined assumptions

Note: True means from simulation marked in blue

To illustrate the properties of this sample size if it were to be analysed within a frequentist framework, the following sample size assessment is also provided:

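### Protocol 9.4.1 gives the Emax slope an unconstrained Normal(0, SD 100) prior and then a second prior on an undefined h, and the 97% precision figure in 9.2.1 holds only with the slope fixed at 1

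*Protocol*

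**What the plan says.** Protocol 9.4.1 models the Week 10 change in Complete Mayo score as Y = E0 + Emax × D^γ / (ED50^γ + D^γ). Dose zero is one of the design points ("Di are doses =0, 45, 150, 300, 450mg and γ is the slope parameter"), and the parameters have stated meanings: "where E0 is the minimum dose effect, Emax is the maximum achievable effect above placebo".

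Two consecutive sentences set the priors. The first is "Initially, normal vague priors will be used for E0, γ and Emax: Normal(0, sd=100", with no restriction to positive slopes. The second is "A functional uniform prior will be used for ED50 and h". The symbol h appears nowhere in the model and is presumably the slope.

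More detail is promised elsewhere: "Further details of the Emax model will be defined in the RAP", and "The parameterisation of the priors used in the analysis will be reported in the clinical study report".

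The parameters are themselves objects of inference. Protocol 9.1 says "The dose response relationship will be characterised using the posterior probabilities of the parameters of an Emax model", together with the estimated response at each dose. It also describes a well-fitted model as one whose 95% credible interval for the response at ED90 has a half-width of at most 1. Protocol 9.2.1 reports that this is met in 97% of simulated trials. In that simulation "the Emax is taken as -3, γ is assumed to be 1 and ED50 is assumed to be 100", and a prior is listed for E0, Emax, ED50 and the residual SD, but none for γ.

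**The concern.** Read literally, the slope has two different priors, or else one prior is attached to a parameter that does not exist. An analyst could not code the primary model from this text without making a choice that the text does not make.

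The first of the two priors is also unsuitable. It is symmetric about zero, so half of it lies on slopes for which the formula breaks down at placebo and for which E0 and Emax lose the meanings given to them. The other half is so wide that it favours step-shaped curves.

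At stake are the parameter summaries that protocol 9.1 names as the primary characterisation, and the precision claim that supports the sample size.

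**Working it through.** **Inputs.** From protocol 9.2.1: arm sizes 48 (placebo), 42, 42, 42 and 68 (450 mg), total 242; SD 1.5; E0 = -1, Emax = -3, ED50 = 100, γ = 1; Normal(0, SD 100) priors for E0 and Emax; Beta(0.5, 5.2) scaled to 0–675 for ED50; Gamma(shape 2, rate 0.1) for the SD. From 9.4.1: γ ~ Normal(0, SD 100). Assumption: ED50 keeps the Beta prior of 9.2.1, because the functional uniform prior is not written out.

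**1. Reproduce the 97%.** With γ fixed at 1 and the response at ED90 taken as E0 + 0.9 × Emax, the half-width is at most 1 in 96.7% of 1,500 simulated trials (Monte Carlo error about 0.5 points). Evaluating at a fixed 900 mg instead gives 100%. The stated figure therefore matches the first reading, with the slope held at 1.

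**2. Prior mass.** P(γ < 0) = 0.50. P(|γ| > 10) = 2 × (1 − Φ(10/100)) = 0.92. The same 92% applies to the positive half alone.

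**3. Dose 0.** For γ < 0, 0^γ is a division by zero and the ratio cannot be evaluated. Its limit as the dose tends to 0 is 1. For γ > 0 the placebo mean is simply E0.

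**4. Reflection.** D^(−γ)/(ED50^(−γ) + D^(−γ)) = 1 − D^γ/(ED50^γ + D^γ). So (E0, Emax, γ) and (E0 + Emax, −Emax, −γ) give the same curve at every positive dose, and at dose 0 if the limit is used. At the planning values:

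| E0, Emax, γ, ED50 | 0 mg | 45 mg | 150 mg | 300 mg | 450 mg |
|---|---|---|---|---|---|
| −1, −3, 1, 100 | −1.00 | −1.93 | −2.80 | −3.25 | −3.45 |
| −4, +3, −1, 100 | −1.00 | −1.93 | −2.80 | −3.25 | −3.45 |

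The ratio of the prior densities of the two points is exp(−(26 − 11)/20,000) = 0.9993, where 26 = 16 + 9 + 1 and 11 = 1 + 9 + 1 are the sums of squares of E0, Emax and γ. The prior does not separate them. E0 + 0.9 × Emax is −1 − 2.7 = −3.7 in one and −4 + 2.7 = −1.3 in the other.

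**5. Refit with γ free** (120 simulated trials, medians over trials):

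| | Both signs, limit at dose 0 | γ > 0 only |
|---|---|---|
| Posterior P(γ < 0) | 0.50 in every trial | 0 |
| 95% interval, E0 (truth −1) | −4.84 to −0.69 | −1.56 to −0.61 |
| 95% interval, Emax (truth −3) | −3.87 to 3.90 | −4.23 to −1.73 |
| Half-width at ED90 at most 1 | about 1% | about 59% |
| Mean posterior mass on \|γ\| > 10 | 32% | 32% |
| Half-width of ED50 | 102 | 102 |
| Half-widths of the five dose means | 0.46, 0.50, 0.39, 0.26, 0.32 | 0.46, 0.50, 0.38, 0.26, 0.32 |

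A second refit gave about 4% for the two-sign case, and 48% to 59% with positive slopes only. The error on the 59% is 4 to 5 points.

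**6. A sensible slope prior.** With γ free under lognormal(0, 0.5), or uniform on 0.5 to 10, the criterion is met in about 60% of trials (62% and 63% in one run of 200).

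**The case against.** The strongest reply is that nothing reported depends on this sentence. After termination the SAP (2.1.4, 2.4 and 8.1.1.2) replaces the Emax model for the primary endpoint with a Bayesian regression of 450 mg against placebo. Its efficacy dose-response displays (2.11, 2.13 and 2.23) are marked as not produced. The Emax models left in SAP 15.10.2 are separate PK/PD fits. This stands. A reader might infer that the final primary result is compromised, and the documents do not support that.

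A reader might also infer that the whole dose-response analysis is unidentified, or that the model is undefined at placebo without qualification. Neither follows. The reflection leaves ED50, all dose-level means and all differences from placebo unchanged. The primary estimand in protocol section 3 is the mean change at each dose level. Evaluation at dose 0 fails only for a negative slope. The two problems are also alternatives: software that rejects the undefined values removes the mirror solution, and taking the limit makes the model defined but brings the mirror solution in.

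The 1% to 4% depends on reading the response at ED90 as E0 + 0.9 × Emax. Measured as 90% of the effect from the placebo mean, it is −3.7 in both solutions, and the result falls back to that for positive slopes. Even on the first reading, failure in every trial would be too strong.

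The text is marked as initial and defers detail to the RAP. That carries less weight. The SAP supplies no Emax specification for this endpoint, and reporting the parameterisation in the clinical study report comes too late to settle it beforehand.

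**Conclusion.** The stated rule is wrong as written, within limits. The slope has an unconstrained prior, half of it on inadmissible values, and apparently a second prior under another name. If the limit is taken at dose 0, E0, Emax, the slope sign and E0 + 0.9 × Emax are identified only up to a reflection, and the ED90 criterion is met in about 1% to 4% of trials. If negative slopes are rejected, the prior that remains is still implausibly wide, and roughly a quarter to a third of the posterior stays on slopes above 10 although the true slope is 1.

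It would be tempting to conclude that a better prior restores the 97%. It does not. Most of the loss comes from estimating the slope at all: about 60% with a sensible positive prior is within simulation error of the 59% with positive slopes under SD 100. The 97% therefore describes a model with the slope fixed at 1, whereas 9.4.1 makes the four-parameter model primary.

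These figures rest on the planning values, complete data on all 242 participants and the Beta prior for ED50. With a uniform ED50 prior on 0 to 675 (an assumption), the criterion is met in 1% of trials with both signs and 6% with positive slopes. The point concerns the protocol's planned dose-response analysis, not the two-arm analysis in the SAP.

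**What to change.** In protocol 9.4.1, state that h is the slope γ, delete the Normal(0, SD 100) prior for it, and give it one proper prior restricted to positive values with a plausible scale. Lognormal(0, 0.5) is one example; another is the functional uniform prior jointly with ED50, with the slope bounded (say 0.5 to 10). The exact choice is a matter of judgement, but it should be fixed before unblinding and not first reported in the clinical study report. State also how the response at ED90 is computed.

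In protocol 9.2.1, either say that the 97% assumes a slope fixed at 1, or rerun the simulation with the slope free under the chosen prior and report that figure (about 60% on the checks above).

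The cost is a sentence or two in 9.4.1 and one rerun of an existing simulation. No data collection changes. Whether about 60% is acceptable for the planned sample size is a question the sponsor would then have to answer. The SAP's post-termination analysis needs no change, but any later reuse of this model should carry the correction.

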3. OBJECTIVES, ENDPOINTS AND ESTIMANDS

Objectives	Endpoints
Primary	

 To evaluate the safety and tolerability of repeat doses of GSK2831781 during the Double-Blind Induction Phase. To characterise the efficacy dose-response of GSK2831781 during the Double-Blind Induction Phase. 	
 Incidence of adverse events and serious adverse events during the Double-Blind Induction Phase. Incidence of findings of potential clinical importance¹ during the Double-Blind Induction Phase for: 
 Vital signs. Clinical laboratory values (haematology, clinical chemistry and urinalysis). QTc. Change from baseline in Complete 4-domain Mayo score² at Week 10.
Secondary	

 To evaluate the safety and tolerability of repeat doses of GSK2831781 during the Double-Blind Extended Treatment Phase. 	
 Incidence of adverse events and serious adverse events in the Double-Blind Extended Treatment Phase. Incidence of findings of potential clinical importance⁵ during the Double-Blind Extended Treatment Phase for: 
 Vital signs.

Objectives	Endpoints
	
 ○ Clinical laboratory values (haematology, clinical chemistry and urinalysis). ○ QTc. 
 ● To investigate the effect of repeat doses of GSK2831781 on clinical efficacy including endoscopic mucosal healing during the Double-Blind Induction Phase. ● Adapted Mayo endoscopic score of 0 or 1 at Week 10. ● Adapted Mayo clinical remission³ at Week 10. ● Adapted Mayo clinical response³ at Week 10. ● Symptomatic remission⁴ over time. ● Change from baseline in partial Mayo score over time. ● Change from baseline in Adapted Mayo endoscopic score and Ulcerative Colitis Endoscopic Index of Severity (UCEIS) at Week 10.

 ● To investigate the effect of repeat doses of GSK2831781 on UC histologic disease activity during the Double-Blind Induction Phase. 	
 ● Histological severity as determined by the Robarts Histopathology Index at Week 10. ● Histological severity as determined by the Nancy Histological Index at Week 10. ● Histological severity as determined by the Geboes Histological Index at Week 10.

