8.2.1.2. Ulcerative Colitis Endoscopic Index of Severity

The Ulcerative Colitis Endoscopic Index of Severity (UCEIS) will be used as an additional tool to assess disease activity based on endoscopic vascular pattern, bleeding, erosions and ulcerations (see SRM for detail). It has been shown to accurately reflect overall assessment of endoscopic severity of UC and predict outcomes in severe disease [Xie, 2018]. Its broader range than the Mayo endoscopic score facilitates assessment of the dose-response relationship [Travis, 2012]. The UCEIS will be collected and scored centrally at all time points indicated in the SoA (see Section 1.3).

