## 5.4. Examination of Covariates, Other Strata and Subgroups

### 5.4.1. Covariates and Other Strata

The following list of covariates and other strata will be used in descriptive summaries and statistical analyses of primary and key secondary efficacy endpoints, some of which will also be used for subgroup analyses. Additional covariates and other strata of clinical interest may also be considered. For change from baseline endpoints, the baseline will also be included as a covariate.

Category	Details	Notes
Advanced therapy experience (Stratification factor)	Categorical variable with three levels: 
 
Advanced therapy naïve,
 
Single class of advanced therapy experience
 
Multiple classes of advanced therapy experience
 
	Derived from 'previous UC medications' in medical history.  This is the stratification factor used in RAMOS, recorded at baseline in the eCRF for each participant; in case of conflict between the stratification in RAMOS and medical history, medical history will be used.
TNF failure (Covariate)	Categorical variable with three levels: 
 
No TNF failure
 
Single TNF failure
 
Multiple TNF failures
 
	Derived from medical history, covariate will be used as secondary analysis at primary completion
biologic experience type (Covariate)	Categorical variable with three levels: 
 
Biologic naïve
 
TNF experience (no Vedolizumab)
 
Vedolizumab (including participants who have both TNF and Vedolizumab experience)
 
 
Note: if participant has experience of other biologics, they will be assigned based on experience of TNF and Vedolizumab.
	Derived from medical history. Comparison made as secondary analysis.
Baseline mucosal CD3+LAG3+ cell count (Covariate)	Continuous variable derived from biopsy.  CD3 positive and Lag3 positive cells per mm  of Lamina Propria tissue taken at screening biopsy.	
Duration of disease (Covariate)	Duration of disease, years	If day and month of diagnosis are missing, duration of disease will be calculated by using day=1 and month=July
Baseline Complete Mayo Score	Where the endpoint is derived from a version of the Mayo score, that version's baseline will be used.	

Category	Details	Notes
Baseline Adapted Mayo Score	Where the endpoint is derived from a version of the Mayo score, that version's baseline will be used.	

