#### 8.2.2. Other Secondary Endpoints - Categorical

The ICE strategy for the Key Secondary Estimand described in Section 8.2.1.1 above will be replicated in the following secondary Efficacy endpoints:

Endpoint	Endpoint name to be displayed for Estimand Analysis
Adapted Mayo Clinical Remission at Week 10	Secondary – Adapted Mayo Clinical Remission
Adapted Mayo Clinical Response at Week 10	Secondary – Adapted Mayo Clinical Response
Symptomatic Remission at Week 10	Secondary – Symptomatic Remission

The “Secondary Estimand – Clinical Remission” will be analysed by replicating the statistical model described in Section 8.2.1.2 above. The other two estimands in the table above will be summarised only.

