### 8.2.3. Other Secondary Endpoints - Continuous

The ICE strategy for the Primary Estimand described in Section 8.1.1.1 above will be replicated in the following secondary Efficacy endpoints:

Endpoint	Endpoint name to be displayed for Estimand Analysis
Change from Baseline in Partial Mayo Score at Weeks 2, 4, 6, 10	Secondary – Partial Mayo Score
Change from Baseline in Adapted Mayo Score at Week 10	Secondary – Adapted Mayo Score
Change from Baseline in Adapted Mayo endoscopic score at Week 10	Secondary – Endoscopic Score
Change from Baseline in UCEIS at Week 10	Secondary – UCEIS Total Score

The four estimands in the table above will be summarised in tables.

In addition, a Bayesian repeated measures analysis will be conducted for the Partial Mayo score, the estimand is described below and the analysis details below that.

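### The protocol commits the secondary endpoints to primary-style modelling, but the SAP only summarises four of them by arm, plans no treatment difference for them, and does not declare the change

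*Protocol*

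**What the plan says.** Protocol section 9.4.1, in the row for secondary endpoints: "Analyses of the secondary endpoints will be conducted using similar methodology as for the primary endpoint". The sentence goes on to require a suitable link function for binary outcomes. Protocol section 9.1 adds: "The dose-response relationship will also be assessed for selected categorical secondary endpoints (Endoscopic Improvement, Clinical Response and Clinical Remission"; symptomatic remission is not in that list. The secondary endpoints in protocol section 3 include adapted Mayo clinical response, symptomatic remission, and "Change from baseline in Adapted Mayo endoscopic score and Ulcerative Colitis Endoscopic Index of Severity (UCEIS) at Week 10".

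SAP section 8.2.2 lists three further categorical secondaries. It applies the section 8.2.1.2 logistic model to clinical remission, then says of clinical response and symptomatic remission: "The other two estimands in the table above will be summarised only". SAP section 8.2.3 lists Partial Mayo, Adapted Mayo, endoscopic score and UCEIS and says: "The four estimands in the table above will be summarised in tables". It adds a Bayesian repeated measures model for Partial Mayo alone.

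SAP section 2.1.4 records that the primary Complete Mayo model now covers only 450 mg and placebo. It mentions the other secondary endpoints only to say that estimands have been defined for them.

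**The concern.** All four endpoints are protocol secondaries, and the protocol describes model-based analysis for secondaries as a group. Under the SAP, a reader who wants the effect of 450 mg on UCEIS or on clinical response must subtract one arm's summary from the other's. No planned interval goes with that subtraction, and neither baseline nor prior advanced therapy (a stratification factor) is adjusted for.

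The gap also touches the estimands. Sections 8.2.2 and 8.2.3 carry over the intercurrent event strategies, so results after discontinuation for COVID-19 or for sponsor termination are set to missing. Sections 8.1.1.1 and 8.2.1.1 justify this by saying that missing at random is built into the Bayesian analysis. These four endpoints have no such analysis. A per-arm summary of observed values conditions on nothing but arm.

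Because the departure is not listed among the changes, a reader of the study report could not tell a deliberate reduction in scope from an oversight.

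**Working it through.** **Text comparison.** No stated figure is in dispute, so the main check sets the documents side by side, using the display list in SAP Appendix 12.

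| Week 10 secondary endpoint | Protocol commitment | SAP analysis | SAP displays |
|---|---|---|---|
| Endoscopic improvement (key secondary) | 9.1, 9.4.1 | Logistic model, 8.2.1.2 | Table 2.21 |
| Clinical remission | 9.1, 9.4.1 | Same model, 8.2.2 | Table 2.21 |
| Partial Mayo change | 9.4.1 | Repeated measures model, 8.2.3.1 | Table 2.14 |
| Clinical response | 9.1, 9.4.1 | Summary only | Table 2.28 at most; Table 2.23 marked None |
| Symptomatic remission | 9.4.1 | Summary only | Tables 2.17, 2.28 |
| Endoscopic score change | 9.4.1 | Summary only | Tables 2.2, 2.29 |
| UCEIS change | 9.4.1 | Summary only | Tables 2.8, 2.30 |

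Table 2.28 lists no endpoints in its notes, so clinical response is placed there by inference from section 8.2.2. The primary endpoint keeps its model in section 8.1.1.2. Figure 2.2 shows estimated differences from placebo for Complete, Adapted and Partial Mayo, but not for UCEIS or endoscopic score. It also presupposes an Adapted Mayo estimate that section 8.2.3 does not define.

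**How uncertain a bare subtraction would be.** The documents do not give the arm sizes at termination. As an illustration, take the 40 and 20 planned for Interim Analysis 3 (protocol section 9.2.1).

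- Continuous endpoint: unadjusted 95% half-width = 1.96 × √(1/40 + 1/20) = 0.54 SD of the change score.
- Binary endpoint, assuming 20% in both arms: 1.96 × √(0.16/40 + 0.16/20) = 0.215, about 21 percentage points.

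**What baseline adjustment would add (continuous endpoints only).** Let σ be the Week 10 SD, k = baseline SD / Week 10 SD, and ρ the baseline to Week 10 correlation.

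- Variance of the change score: σ²(1 + k² − 2ρk).
- Residual variance after adjusting for baseline: σ²(1 − ρ²).
- Ratio, adjusted to unadjusted: (1 − ρ²) / (1 + k² − 2ρk).

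The documents give neither ρ nor k, so both are assumed:

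| | ρ = 0.2 | ρ = 0.3 | ρ = 0.5 |
|---|---|---|---|
| k = 1 | 0.96/1.60 = 0.60 | 0.91/1.40 = 0.65 | 0.75/1.00 = 0.75 |
| k = 0.67 | 0.96/1.181 = 0.81 | 0.91/1.047 = 0.87 | 0.75/0.779 = 0.96 |
| k = 0.5 | 0.96/1.05 = 0.91 | 0.91/0.95 = 0.96 | 0.75/0.75 = 1.00 |

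The lower rows matter for endoscopic score. Protocol section 5.1 requires a centrally read endoscopic subscore of at least 2 at entry. If the item runs from 0 to 3 (the scoring tables are redacted), baseline can only be 2 or 3 and its SD cannot exceed 0.5. Suppose 20%, 40% and 40% score 1, 2 and 3 at Week 10. The mean is 2.2, the variance 5.4 − 4.84 = 0.56 and the SD 0.75, so k is at most about 0.67.

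**The case against.** The protocol's methodology was a five-group Emax model with prior therapy as the only named factor. It never promised a baseline-adjusted pairwise difference. With too few participants on the middle doses after termination, that model could not be fitted, and SAP section 2.1 attributes most changes to the termination. The dropped dose-response table that named clinical response (Table 2.23) is openly marked None, and sections 8.2.2 and 8.2.3 say plainly that the endpoints are summarised. Endoscopy and symptoms are still modelled through four other endpoints. Choosing which lower secondaries to model in a terminated Phase 2 trial is partly a matter of judgement.

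Much of this stands. It justifies losing the dose-response form and limits the consequence. It does not explain why the 450 mg versus placebo comparison is kept for some endpoints and not these, or why section 2.1.4 is silent. For symptomatic remission the commitment rests on section 9.4.1 alone.

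Four stronger readings are tempting but not supported:

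- A reader might infer that the SAP breaks its own rule, since section 5.4.1 says: "For change from baseline endpoints, the baseline will also be included as a covariate". The paragraph containing that sentence is limited to primary and key secondary endpoints, and these four are neither.
- A reader might infer a general 25–40% variance saving, or its equivalent of 33–67% more participants (1/0.75 and 1/0.60). That needs equal SDs at baseline and Week 10, which the entry criterion makes doubtful for endoscopic score. It does not apply to the binary endpoints.
- A reader might infer that UCEIS was chosen because it shows treatment effects better. Protocol section 8.2.1.2 says: "Its broader range than the Mayo endoscopic score facilitates assessment of the dose-response relationship". That concerns dose-response, which is no longer assessed.
- A reader might infer that no precision is reported at all. Table 2.2 gives standard errors, and Figures 2.6 and 2.9 are forest plots of proportions by arm, which may carry intervals (the mock shells are in a separate document). Only the between-arm contrast is missing.

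**Conclusion.** The point holds as a gap between protocol and SAP. Four protocol secondaries have no planned adjusted 450 mg minus placebo difference and no interval for one, and the change is not declared where changes are listed. This rests on the text alone and needs no numerical assumption.

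The statistical cost is less certain. For the two continuous endpoints, adjustment would leave between 60% and 100% of the unadjusted variance over the assumed grid. The gain is likely to be small for endoscopic score; for UCEIS it is unknown, since entry also selects endoscopically active disease. For the two binary endpoints the loss is the missing contrast and interval, not a quantified loss of precision. The primary and key secondary conclusions are unaffected.

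**What to change.** - **SAP 8.2.3:** fit the section 8.1.1.2 model (450 mg versus placebo) to Week 10 change in UCEIS and in endoscopic score. Give each its own baseline and keep the terms for advanced therapy experience and disease duration. Endoscopic score takes few values, so its normal model should be labelled an approximation.
- **SAP 8.2.2:** fit the section 8.2.1.2 logistic model to clinical response and symptomatic remission. Use a vague placebo prior, for example the Beta(1/3, 1/3) already used for the active arm, because Appendix 14 sets endpoint criteria for historical placebo data only for clinical remission and endoscopic improvement.
- **Reporting:** give the 450 mg minus placebo difference with its 95% credible interval beside the existing summaries.
- **SAP 2.1.4:** state that the two-arm model replaces the protocol's dose-response form for these endpoints. If the sponsor prefers not to add the models, declare and justify that here instead.

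The cost is a few extra runs of models already specified and one or two table pages, with no new data. The drawback is four more contrasts without multiplicity adjustment, consistent with SAP section 5.5; they should be read as estimates and not as tests.
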